Gastrointestinal disorders	Abdominal abscess, abdominal adhesions, abdominal: discomfort/distension/pain/tenderness, anorectal discomfort, anal fissure, anal fistula, anastomotic leak, ascites, colitis, constipation, diarrhea, diverticulum, duodenal ulcer, dyspepsia, dysphagia, esophageal perforation, feces discolored, gastric perforation, gastric ulcer hemorrhage, gastric ulceration, gastrointestinal angiodyplasia, gastrointestinal ischemia, gastrointestinal oedema, gastroenteritis , hemorrhoids, hematemesis, hematochezia, hiccups, ileus, intestinal perforation, melena, mesenteric vein thrombosis, mouth ulceration, nausea, pancreatitis, proctalgia, proctitis, recall phenomenon radiation enteritis, rectal discharge/hemorrhage, small intestinal obstruction, stomatitis, swollen tongue, vomiting, oral pain, enterovesical fistula, radiation esophagitis, necrotizing esophagitis, salivary gland calculus, small bowel thickness, thickened bowel Wall Gastritis: erosive/ hemorrhagic Lip: edema/swelling/ulceration Gastrointestinal: disorder/hemorrhage/sounds Mucosal: hemorrhage/inflammation
General disorders and administration site conditions	Application site erythema, asthenia, bloody discharge, calcinosis, chest discomfort/pain, chills, concomitant disease progression, condition aggravated, crepitations, death, discomfort, disease progression, drug ineffective, and drug withdrawal syndrome (asthenia and flushing) edema peripheral, face edema, facial pain, fatigue, feeling of body temperature change, general physical health deterioration, generalized edema, goiter , granuloma, hypertrophy, hypothermia, impaired healing, inflammation, influenza like illness, irritability, local swelling, malaise, mass, multi-organ failure, necrosis, non-cardiac chest pain, pain, performance status decreased, pitting edema, pyrexia, sudden death, swelling, tenderness, thirst
Hepatobiliary disorders	Cholecystitis, cholelithiasis, cholestasis, cytolytic hepatitis, hepatic cirrhosis, hepatic failure , hepatic function abnormal, hepatic necrosis, hepatorenal failure , hepatitis B and C reactivation, hepatomegaly, hyperbilirubinemia, jaundice, portal vein thrombosis
Immune system disorders	Acute disseminated encephalomyelitis, autoimmune disorder, cytokine release syndrome, Guillain Barre syndrome, hypersensitivity, immunosuppression, Stevens-Johnson syndrome
Infections and infestations	Bronchitis, bronchopneumonia, bronchopulmonary aspergillosis. candida sepsis, cellulitis, citrobacter sepsis, clostridium bacteremia, endocarditis, escherichia bacteremia, folliculitis, gastroenteritis, hepatitis fulminant. infected lymphocele, klebsiella sepsis, liver abscess, meningitis, herpes, nasopharyngitis, neutropenic sepsis, perirectal/anal abscess, pharyngitis, pneumococcal sepsis, pseudomonal bacteremia, purulent discharge, pyelonephritis, respiratory moniliasis, sepsis syndrome, septic shock, sinusitis, staphylococcal bacteremia, staphylococcal sepsis, streptococcal bacteremia, tonsillitis, tuberculosis, urosepsis Infection(s): alpha hemolytic streptococcal/atypical mycobacterium/bacterium/clostridium/enterobacter/enterococcal/epstein-barr virus/escherichia/escherichia urinary tract/gastrointestinal/haemophilus/herpesvirus/general/ localized/ morganella/ proteus/ skin/streptococcal/staphylococcal/urinary tract/ wound staphylococcal
Injury, poisoning and Procedural complications	Abdominal adhesion, anastomotic leak, bone fissure, collapse of lung, contusion, eschar, fall, head injury, lung injury, medical device complication, medication error, post procedural swelling, recall phenomenon radiation enteritis, surgical procedure repeated, vena cava injury, wound dehiscence/secretion
Investigations	Aspiration pleural cavity, antinuclear antibody positive, bleeding time prolonged, breath sounds abnormal, cardiac function test abnormal, chest X-ray abnormal, clostridium difficile toxin test positive, computerised tomogram abnormal, ejection fraction decreased, endoscopy upper gastrointestinal tract, general physical condition abnormal, granulocyte count decreased, hematocrit/hemoglobin decreased, hypophosphatemia, liver function test abnormal, neutrophil count

	abnormal/decreased, occult blood positive, oxygen saturation abnormal/decreased, peak expiratory flow rate decreased, protein urine present, QRS axis abnormal, urine output decreased, X-ray abnormal; Increased: alanine aminotransferase, ammonia, aspartate aminotransferase, aspartate aminotransferase, body temperature, C-reactive protein, eosinophil count, gamma-glutamyltransferase, international normalised ratio, lipase, red blood cell count, sedimentation rate, transaminases, troponin T, troponin Platelet count: abnormal/decreased/increased White blood cell(s): count abnormal/decreased/in urine Lymphocyte count: decreased/increased Blood: amylase increased/albumin decreased/alkaline phosphatase increased/bilirubin increased/ creatinine phosphokinase increased/creatinine increased/magnesium decreased/glucose increased/lactate dehydrogenase increased/potassium decreased/pressure diastolic decreased/pressure orthostatic abnormal/pressure systolic decreased/triglycerides increased/urea increased/urine present Electrocardiogram: T wave abnormal/T wave amplitude decreased/poor R-wave progression Weight: decreased/ increased
Metabolism and nutrition disorders	Acidosis, anorexia, appetite disorder, cachexia, cushing's syndrome , decreased appetite, dehydration, diabetes mellitus, diabetic ketoacidosis, electrolyte imbalance, failure to thrive, fluid overload/retention, food intolerance, glucose tolerance impaired, gout, hypothyroidism, malnutrition, metabolic acidosis, oral intake reduced, polydipsia, type 2 diabetes mellitus Hyper: cholesterolemia/glycemia/kalemia/lipidemia/calcaemia uricemia/triglyceridemia, glycemic non-ketotic syndrome Hypo: calcemia/glycemia/kalemia/magnesemia/natremia/ proteinemia/hypophosphatemia
Musculoskeletal and connective tissue disorders	Arthritis, bone fissure, fistula, gout mobility decreased, joint effusion, rhabdomyolysis Pain: back/flank/musculoskeletal/musculoskeletal chest/extremity/neck Muscle: spasms/weakness; myalgia, arthralgia Osteoarthritis; Osteonecrosis, Osteoreadionecrosis
Neoplasms benign, malignant and unspecified (incl cysts and polyps)	Acute leukemia, adenocarcinoma of pancreas, Burkitt's lymphoma, carcinoid syndrome, colon neoplasm, lung neoplasm, lymphoproliferative disorder, malignant neoplasm progression, malignant melanoma , malignant pleural effusion, pancreatic carcinoma , squamous cell carcinoma of skin, uterine leiomyoma Metastases: central nervous system/lung/lymph nodes/neoplasm; Tumor: hemorrhage/necrosis
Nervous system disorders	Acute disseminated encephalomyelitis, asterixis, ataxia, cerebrovascular accident, cognitive disorder, complex partial seizures, complex regional pain syndrome, convulsion, depressed level of consciousness, dizziness, dysuria, encephalitis, encephalopathy, facial palsy, headache, hemiparesis, hemiplegia, hyperglycemic non-ketotic syndrome, hypersomnia, hypoglycemic coma, lethargy, loss of consciousness, ophthalmoplegia_crani nerve paralysis, neuralgia, neuropathy peripheral, presyncope, sinus headache, somnolence, speech disorder, tremor, vertigo Cerebral: hemorrhage/ infarction/ischemia; transient ischemic attack
Psychiatric disorders	Agitated depression, anxiety, confusional state, delirium, delusional disorder, disorientation, drug withdrawal syndrome, libido decreased insomnia, mental disorder/status changes, mood altered, persecutory type, personality disorder , neurosis, staring
Renal and urinary disorders	Acute renal failure, anuria, bladder tamponade, dysuria, hematuria, hemolytic uremic syndrome, hydronephrosis, leukocyturia, nephrolithiasis, oliguria, pollakiuria, polyuria, postrenal failure, renal failure/acute/impairment, urinary bladder hemorrhage, urinary incontinence, renal atrophy, renal colic, renal tubular necrosis
Reproductive/breast disorders	Azospermia, endometrial hyperplasia , libido decreased, menorrhagia , pelvic pain, ovarian cyst, scrotal edema
Respiratory, thoracic and mediastinal disorders	Alveolitis, alveolitis allergic, asthma, atelectasis, bronchomalacia, bronchospasm, cough, cryptogenic organizing pneumonia, diffuse alveolar damage, dysphonia, dyspnea/dyspnea exertional, emphysema, epistaxis, hemoptysis, hydrothorax, hypercapnia, hypoxia, laryngeal edema, interstitial lung disease, laryngeal inflammation, pneumothorax, rales, sinus congestion, stridor, tachypnea, wheezing Acute: respiratory distress syndrome/respiratory failure Lung: consolidation/disorder/infiltration, obstructive airways disorder, orthopnoea, pharyngolaryngeal pain, pleural disorder/effusion/pleurisy/pain; pneumonia aspiration, pneumonitis, pneumothorax, productive cough, rhinorrhea

	Pulmonary: congestion/alveolar/hemorrhage/artery dilatation/cavitation/embolism/fibrosis/haemorrhage/hypertension/edema/toxicity Respiratory: arrest/disorder/distress/failure/gas exchange disorder
Skin and subcutaneous tissue disorders	Acute febrile neutrophilic dermatosis, Angioedema, blister, dermatitis, dermatitis acneiform, erythema, hyperhidrosis, leukocytoclastic vasculitis, night sweats, petechiae, photosensitivity reaction, pruritus, Stevens-Johnson syndrome Rash: erythematous/generalized/maculo-papular/pruritic/skin disorder/exfoliation/lesion/reaction/ulcer/palmar plantar erythrodysesthesia/hand foot syndrome
Surgical and medical procedures	Abscess drainage, biliary drainage, bladder irrigation, catheter removal, chest tube insertion, cholecystectomy, debridement, endotracheal intubation, fistula repair, gastric ulcer surgery, gastrointestinal tube insertion, ileojejunal bypass, incisional drainage, laparotomy, mechanical ventilation, pleurodesis, sinus operation, surgery, thoracic cavity drainage, tracheostomy Pericardial: drainage/excision/operation Wound: closure/drainage/treatment
Vascular disorders	Capillary leak syndrome, circulatory collapse, embolism, flushing, gastrointestinal angiodyplasia, gastrointestinal ischaemia, haemorrhoids, hematoma, hemodynamic instability, hemorrhage, hypertension, hypertensive angiopathy, hypertensive crisis, hypotension, lymphangiopathy, lymphedema, pallor, shock; transient ischemic attack, retinal hemorrhage, Thrombosis: deep vein/jugular vein

*New events added to IB Editions 12 and 13 are noted in bold

8.1.2 Laboratory test abnormalities

Laboratory abnormalities that constitute an Adverse event in their own right (are considered clinically significant, induce clinical signs or symptoms, require concomitant therapy or require changes in study treatment), should be recorded on the Adverse Events CRF. Whenever possible, a diagnosis, rather than a symptom should be provided (e.g. anemia instead of low hemoglobin). Laboratory abnormalities that meet the criteria for Adverse Events should be followed until they have returned to normal or an adequate explanation of the abnormality is found. When an abnormal laboratory or test result corresponds to a sign/symptom of an already reported adverse event, it is not necessary to separately record the lab/test result as an additional event.

Laboratory abnormalities, that do not meet the definition of an adverse event, should not be reported as adverse events. A Grade 3 or 4 event (severe) as per CTCAE does not automatically indicate a SAE unless it meets the definition of serious as defined below and/or as per investigator's discretion. A dose hold or medication for the lab abnormality may be required by the protocol and is still, by definition, an adverse event.

8.2 Serious Adverse Events

8.2.1 Definitions

A serious adverse event is an undesirable sign, symptom or medical condition which:

- is fatal or life-threatening
- results in persistent or significant disability/incapacity
- constitutes a congenital anomaly/birth defect
- requires inpatient hospitalization or prolongation of existing hospitalization, unless hospitalization is for:

IRB NUMBER: PHXB-17-0072-70-15
IRB APPROVAL DATE: 07/03/2018

Dignity Health
Research Institute

- routine treatment or monitoring of the studied indication, not associated with any deterioration in condition (specify what this includes)
- elective or pre-planned treatment for a pre-existing condition that is unrelated to the indication under study and has not worsened since the start of study drug
- treatment on an emergency outpatient basis for an event not fulfilling any of the definitions of a SAE given above and not resulting in hospital admission
- social reasons and respite care in the absence of any deterioration in the patient's general condition
- is medically significant, i.e., defined as an event that jeopardizes the patient or may require medical or surgical intervention to prevent one of the outcomes listed above

8.2.2 Reporting

The principal investigator has the obligation to report all serious adverse events to the FDA, IRB, and Novartis Pharmaceuticals Drug Safety and Epidemiology Department (DS&E) (***For patients taking Novartis drugs***).

All events reported to the FDA by the investigator are to be filed utilizing the Form FDA 3500A (MedWatch Form).

To ensure patient safety, every SAE, regardless of suspected causality, occurring after the patient has provided informed consent and until at least 30 days after the patient has stopped study treatment/participation must be reported to Novartis within 24 hours of learning of its occurrence. Information about all SAEs is collected and recorded on a Serious Adverse Event Report Form. The investigator must assess and record the relationship of each SAE to each specific study treatment (if there is more than one study treatment), complete the SAE Report Form in English, and **send the completed, signed form along with the Novartis provided fax cover sheet to the Novartis Oncology Drug Safety and Epidemiology (DS&E) department by fax ([contact]) within 24 hours**.

Any additional information for the SAE including complications, progression of the initial SAE, and recurrent episodes must be reported as follow-up to the original episode within 24 hours of the investigator receiving the follow-up information. An SAE occurring at a different time interval or otherwise considered completely unrelated to a previously reported one should be reported separately as a new event.

Any SAEs experienced after this 30 days period should only be reported to Novartis if the investigator suspects a causal relationship to the study drug. Follow-up information is submitted in the same way as the original SAE Report. Each re-occurrence, complication, or progression of the original event should be reported as a follow-up to that event regardless of when it occurs. The follow-up information should describe whether the event has resolved or continues, if and how it was treated, whether the blind was broken or not, and whether the patient continued or withdrew from study participation.

If the SAE is not previously documented in the Everolimus Investigator Brochure or Package Insert (new occurrence) and is thought to be related to the Novartis study drug, a DS&E associate may urgently require further information from the investigator for Health Authority reporting. Novartis may need to issue an Investigator Notification (IN), to inform all investigators involved in any study with the same drug that this SAE has been reported. Suspected Unexpected Serious Adverse Reactions (SUSARs) will be collected and reported to the competent authorities and relevant ethics committees

in accordance with Directive 2001/20/EC or as per national regulatory requirements in participating countries.

All serious adverse events and any deaths will be reported to the DSMB and to the University of Arizona Human Subjects Protection Program per the guidelines set forth in University of Arizona Cancer Center Data and Safety Monitoring Board Charter, Table 5: Adverse Event Reporting.

All submitted serious adverse events will be processed by the DSMB Coordinator monthly for initial trend analysis and then reviewed by the DSMB Chair. The assigned QA/QC Monitor will review the SAE reporting process to confirm reporting requirements are met.

8.3 Pregnancy

To ensure patient safety, each pregnancy occurring while the patient is on study treatment must be reported to Novartis within 24 hours of learning of its occurrence. The pregnancy should be followed up to determine outcome, including spontaneous or voluntary termination, details of the birth, and the presence or absence of any birth defects, congenital abnormalities, or maternal and/or newborn complications.

Pregnancy should be reported by the investigator to the oncology Novartis Drug Safety and Epidemiology Department (DS&E) by fax (**[contact]**). Pregnancy follow-up should include an assessment of the possible relationship to the investigational/study treatment and any pregnancy outcome. Any SAE experienced during pregnancy must be reported on the SAE Report Form.

Pregnancy outcomes must be collected for the female partners of any males who took study treatment in this study. Consent to report information regarding these pregnancy outcomes should be obtained from the mother.

9 Statistical methods

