Premature patient withdrawal	Point/time when the patient exits from the study prior to the planned completion of all study treatment administration and/or assessments; at this time all study treatment administration is discontinued and no further assessments are planned, unless the patient will be followed for progression and/or survival
Stop study participation	Point/time at which the patient came in for a final evaluation visit or when study treatment was discontinued whichever is later
Study treatment	
Includes any drug or combination of drugs in any study arm administered to the patient (subject) as part of the required study procedures, including placebo and active drug run-ins.
 
In specific examples, it is important to judge investigational treatment component relationship relative to a study treatment combination; study treatment in this case refers to the investigational and non-investigational treatments in combination.

Study treatment discontinuation	Point/time when patient permanently stops taking study treatment for any reason; may or may not also be the point/time of premature patient withdrawal
Supportive treatment	Refers to any treatment required by the exposure to a study treatment, e.g. premedication of vitamin supplementation and corticosteroid for pemetrexed disodium.
Variable	Identifier used in the data analysis; derived directly or indirectly from data collected using specified assessments at specified time points

Schema

Step 1¹

R
E
G
I
S
T
E
R

RT or chemoRT
administration

Step 2²

R
E
G
I
S
T
E
R

Everolimus
Administration³

↓↓↓↓

CORRELATIVE STUDIES⁴

¹ Patients with locally advanced squamous cell carcinoma of the Head and Neck treated with curative intent either in the post-operative or definitive setting with high dose radiotherapy (RT ≥ 50 Gy) with or without chemotherapy (chemoRT) will be eligible

² Verify eligibility for everolimus treatment. Patients with clinically severe gland dysfunction (i.e., those with loss of at least 50% of the pre-radiotherapy value) will be eligible for everolimus treatment.

³ Everolimus (5 or 10 mg) po qd, x 5days only, starting 2 weeks after definitive treatment completion

⁴ Saliva flow rates and xerostomia surveys will be obtained at baseline, after 3 and 6 weeks of RT/chemoRT, prior to everolimus administration, at completion of the 5 day everolimus course and at 1,3 and 6 months after RT/chemoRT completion

1 Background

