The potential reproductive risk for humans is unknown. However, due to the observed malformations in rats, everolimus should be considered potentially teratogenic. Everolimus should not be given to pregnant women unless the potential benefit outweighs the potential risk for the fetus. Women of childbearing potential should be advised to use highly effective contraception methods while they are receiving everolimus and up to 8 weeks after treatment has been stopped. It is not known whether everolimus is excreted in human milk. In animal studies, everolimus and/or its metabolites were readily transferred into the milk of lactating rats. Therefore women who are taking everolimus should not breastfeed.

Further details can be found in the Everolimus Investigator's Brochure.

2 Rationale

[name] and colleagues developed a mouse model to study the effects of salivary gland radiation on glandular functions. Analysis of salivary gland cell proliferation and apoptosis in irradiated mice demonstrated that expression of Akt or treatment with IGF-1 protected irradiated salivary glands; the protective effect of IGF-1 was dependent on autophagy, as evidenced by the lack of protection in IGF-1 treated mice in which Atg5 was conditionally deleted in the salivary gland. Subsequently, [name] and colleagues showed that mice irradiated with a single dose of radiation (5Gy) and treated with the mTOR inhibitor CCI-779 for five days (experimental days 4-8) had salivary flow rates and amylase secretion similar to unirradiated controls and statistically increased when compared to irradiated mice (Morgan-Bathke 2014). A follow-up mouse pilot study was conducted with a radiation regimen of 2 Gy/day for 5 consecutive days followed by three injections of CCI-779 at four (experimental days 9-11), fourteen (experimental days 22-24) or 30 days (experimental days 38-40) after the last radiation treatment. Preliminary analysis at 60 days post-radiation suggests that **administration of CCI-779 four or fourteen days after radiation leads to improved salivary output** while administration 30 days later did not produce an improvement.

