4. Uncontrolled diabetes mellitus as defined by HbA1c $> 8\%$ despite adequate therapy. Patients with a known history of impaired fasting glucose or diabetes mellitus (DM) may be included, however blood glucose and antidiabetic treatment must be monitored closely throughout the trial and adjusted as necessary;
5. Patients who have any severe and/or uncontrolled medical conditions such as:
 - a. unstable angina pectoris, symptomatic congestive heart failure, myocardial infarction ≤ 6 months prior to start of Everolimus, serious uncontrolled cardiac arrhythmia, or any other clinically significant cardiac disease
 - b. Symptomatic congestive heart failure of New York heart Association Class III or IV
 - c. active (acute or chronic) or uncontrolled severe infection, liver disease such as cirrhosis, decompensated liver disease, and active and chronic hepatitis (i.e. quantifiable HBV-DNA and/or positive HbsAg, quantifiable HCV-RNA),
 - d. known severely impaired lung function (spirometry and DLCO 50% or less of normal and O₂ saturation 88% or less at rest on room air),
 - e. active, bleeding diathesis;

6. Chronic treatment with corticosteroids or other immunosuppressive agents. Topical or inhaled corticosteroids are allowed;
7. Known history of HIV seropositivity;
8. Patients who have received live attenuated vaccines within 1 week of start of Everolimus and during the study. Patient should also avoid close contact with others who have received live attenuated vaccines. Examples of live attenuated vaccines include intranasal influenza, measles, mumps, rubella, oral polio, BCG, yellow fever, varicella and TY21a typhoid vaccines;
9. Patients who have a history of another primary malignancy, with the exceptions of: non-melanoma skin cancer, and carcinoma in situ of the cervix, uteri, or breast from which the patient has been disease free for ≥ 3 years;
10. Patients with a history of non-compliance to medical regimens or who are considered potentially unreliable or will not be able to complete the entire study;
11. Patients who are currently part of or have participated in any clinical investigation with an investigational drug within 1 month prior to dosing;
12. Pregnant or nursing (lactating) women;

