7.1 Study flow and visit schedule

Table 7-1 Visit evaluation schedule

	Screening / Baseline	RT Day 22	RT Day 43	Post RT day 15	Post RT day 22	Post RT week 6	Post RT week 14	Post RT week 26
Visit no.	1	2	3	4	5	6	7	8
Treatment days*	-21 to -1							
Demography/informed consent (D)	X							
Inclusion/exclusion criteria (D)	X							
Relevant medical history/current medical conditions (D)	X							
Diagnosis and extent of cancer (D)	X							
Prior/post antineoplastic therapy (D)	X							
HIV history (S)	X							
Vital signs (D)	X	X	X	X	X	X	X	X
Height (D)	X							
Weight (D)	X	X	X	X	X	X	X	X
Physical examination (S)	X	X	X	X	X	X	X	X
ECOG performance status (D)	X	X			X	X	X	X
EKG ¹ (D)			X					
Correlative studies	X	X	X	X	X	X	X	X
Hematology ² (D)	X		X	X	X			
Coagulation (D)	X		X	X	X			
Biochemistry ³ (D)	X		X	X	X			
Serum Lipid Profile ⁴ (D)	X		X	X	X			
Prior/concomitant medications (D)	X			X	X			

	Screening / Baseline	RT Day 22	RT Day 43	Post RT day 15	Post RT day 22	Post RT week 6	Post RT week 14	Post RT week 26
Visit no.	1	2	3	4	5	6	7	8
Treatment days*	-21 to -1							
Everolimus ⁵				X				
HBV-DNA, HBsAg, HBs Ab, HBc Ab, HCV-RNA-PCR ⁶ (D)	X							
HBV DNA, HCV RNA-PCR ⁷ (D)	X							

* (+/- 1 day for visits 2,3,4,5; +/- 1 week for visits 6,7,8)

1. Baseline ECG is a standard 12 lead and must be performed within 21 days of first dose for patients enrolled and may be repeated at the investigator's discretion if clinically indicated
2. Hematology tests include a complete blood count (CBC). A total white blood cell (WBC) with absolute differentials (including neutrophil count plus bands, lymphocyte, monocyte, eosinophil, basophil counts), red blood cells (RBC), hemoglobin (Hgb), and a platelet count.
3. Serum Chemistry must include: BUN or uric acid, creatinine, LDH, total protein, electrolytes (sodium, potassium and calcium), total bilirubin, GGT, albumin, alkaline phosphatase, AST/sGOT fasting glucose.
4. Serum fasting lipid profile must include: total cholesterol and triglycerides. Patients should be in fasting state.
5. Everolimus is taken once daily for a total of five days, with drug dispensed at Visit 4.

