7.2 Assessment types

7.2.1 Pregnancy and assessments of fertility

There are no adequate data from the use of everolimus in pregnant women. Studies in animals have shown reproductive toxicity effects including embryo-toxicity and feto-toxicity. The potential risk for humans is unknown. Everolimus should not be given to pregnant women unless the potential benefit outweighs the potential risk to the fetus. If a pregnancy occurs while on study treatment, the newborn will be followed for at least 12 months.

It is not known whether everolimus is excreted in breast milk. However, in animal studies everolimus and/or its metabolites readily passed into the milk of lactating rats. Women taking everolimus should therefore not breast-feed.

Women of childbearing potential

Women of child-bearing potential, defined as all women physiologically capable of becoming pregnant, (including female pediatric patients who are menarcheal or who become menarcheal during the treatment) must use highly effective contraception during the study and for 8 weeks after stopping treatment. Highly effective contraception is defined as either:

- Total abstinence: When this is in line with the preferred and usual lifestyle of the subject. [Periodic abstinence (e.g., calendar, ovulation, symptothermal, post-ovulation methods) and withdrawal are not acceptable methods of contraception]
- Female Sterilization: have had surgical bilateral oophorectomy (with or without hysterectomy), total hysterectomy or tubal ligation at least six weeks before taking study treatment. In case of oophorectomy alone, only when the reproductive status of the woman has been confirmed by follow up hormone level assessment
- Male partner sterilization: The vasectomized male partner should be the sole partner for that subject with the appropriate post-vasectomy documentation of the absence of sperm in the ejaculate.
- Use of oral, injected or implanted hormonal methods of contraception or placement of an intrauterine device (IUD) or intrauterine system (IUS) or other forms of hormonal contraception that have comparable efficacy (failure rate <1%), for example, hormone vaginal ring or transdermal hormone contraception. In case of use of oral contraception women should have been stable on the oral agent for a minimum of 3 months before taking everolimus.

Male Contraception

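### For female participants, pregnancy reporting and newborn follow-up are triggered only during five dosing days, not the 8 weeks of required contraception that follow; how pregnancy is ruled out before dosing is also unstated

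*Protocol*

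**What the plan says.** Pregnancy reporting and follow-up:

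- Section 8.3: "each pregnancy occurring while the patient is on study treatment must be reported to Novartis within 24 hours of learning of its occurrence".
- Section 7.2.1: "If a pregnancy occurs while on study treatment, the newborn will be followed for at least 12 months".
- Section 8.3 also requires pregnancy outcomes to be collected for female partners of men who took study treatment. It sets no time limit on this.

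Study treatment and its length:

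- The Glossary says that study treatment "Includes any drug or combination of drugs in any study arm administered to the patient (subject) as part of the required study procedures".
- Table 7-1, note 5: "Everolimus is taken once daily for a total of five days, with drug dispensed at Visit 4".

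The hazard and the precaution:

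- Section 1.2.1.2 states that "due to the observed malformations in rats, everolimus should be considered potentially teratogenic".
- Section 7.2.1 says that women of child-bearing potential "must use highly effective contraception during the study and for 8 weeks after stopping treatment". Section 1.2.1.2 and exclusion 13 in Section 5.1 carry the same 8 weeks.

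Eligibility:

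- Exclusion 12 in Section 5.1 reads "Pregnant or nursing (lactating) women".
- Table 7-1 marks the inclusion and exclusion criteria at Visit 1 only. Neither the table nor its notes list a pregnancy test, and Sections 5.1 and 7.2.1 do not name one.
- The Schema has a second registration at which eligibility for everolimus is verified. Its footnote mentions only salivary gland dysfunction.

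**The concern.** A trigger limited to time on treatment suits a drug taken continuously for months. Applied to a five-day course it is very short, while the protocol's own precaution against pregnancy runs for a further 8 weeks. The protocol thus treats conception in those weeks as something to prevent, yet does not require anyone to be told if it happens or the child to be followed.

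The stake is the completeness of safety data on a drug that the protocol itself treats as potentially harmful to a fetus. No endpoint, sample size or analysis is affected.

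A second, separate gap concerns exclusion 12. It depends on knowing whether a woman is pregnant, and the document does not show how or when that is established before she is exposed.

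**Working it through.** No figure in the protocol needs to be reproduced. The check is a comparison of periods and a day count.

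**Length of the trigger.** Study treatment means drugs given as part of the required study procedures, which here is everolimus for 5 days. Radiotherapy and chemotherapy are the curative treatment that patients receive before it. Even if that chemotherapy were counted as study treatment, it ends before everolimus starts, so the period after the last dose would stay uncovered.

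**Length of the contraception period, counted from first dose.**

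- 8 weeks × 7 = 56 days after stopping.
- 5 + 56 = 61 days in all.
- Covered by the trigger: 5 / 61 = 8.2%.
- Not covered: 56 / 61 = 91.8%.

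The 61 days are the shorter reading. Section 7.2.1 and exclusion 13 also require contraception during the study as a whole.

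**Comparison with the SAE window.** Section 8.2.2 collects SAEs until at least 30 days after stopping, so at least 5 + 30 = 35 days from first dose. The pregnancy trigger is shorter than this too.

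**Which cases fall in the gap.**

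| Case | Required by the text? |
|---|---|
| Female participant already pregnant at dosing, or conceiving during the five days | Arguably yes: the pregnancy occurs on treatment and is reportable once learned of |
| Female participant conceiving within 8 weeks after the last dose | No pregnancy report, no newborn follow-up |
| Female partner of a treated man | Outcome collected, no time limit |
| Congenital anomaly or other serious outcome | Captured under the SAE rules of Sections 8.2.1 and 8.2.2; after 30 days only if suspected to be drug-related |

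The gap is the second row.

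**Where the 8 weeks end in the schedule.** With the first dose on post-RT day 15, the last is on day 15 + 4 = 19, and 19 + 56 = day 75. Visit 6 is at week 6 (day 42) and Visit 7 at week 14 (day 98), so existing visits fall on either side.

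**Interval from the eligibility check to dosing.** Assume that screening days −21 to −1 count from the start of RT and that RT ends near RT Day 43. Dosing then falls at about day 43 + 15 = 58.

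- From day −1: 58 + 1 = 59 days, about 8.4 weeks.
- From day −21: 58 + 21 = 79 days, about 11.3 weeks.

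No scheduled pregnancy test falls in that interval or at either end of it.

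**The case against.** The case for leaving the text alone has several parts, and much of it is sound.

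- **Partners are covered.** A reader might infer that partners of treated men are also outside the rule. Section 8.3 does not support that: their pregnancy outcomes are collected without a time limit. Giving partners an 8-week window would narrow what is there now.
- **Pregnancies present at dosing are arguably covered.** Section 8.3 counts 24 hours from learning of the pregnancy. One that began during chemoradiation and continued through the five doses can be read as occurring on treatment. The absence of a test bears on preventing exposure, not on whether such a pregnancy is reportable.
- **The day ratio is not a rate of missed events.** A reader might infer that about 92% of exposed pregnancies would be lost. The documents do not support this. The ratio compares calendar days, and the protocol labels the 8 weeks a contraception period, not a measured period of fetal risk.
- **There are backstops.** A congenital anomaly is an SAE, and a late SAE suspected to be drug-related remains reportable. The SAE window also refers to the end of participation, which the Glossary can place at the final visit. Contraception is required during the study, so also during chemoradiation.
- **Eligibility is looked at again.** Step 2 verifies eligibility before everolimus. Table 7-1 is also not exhaustive: it has no adverse-event row, although Section 8.1.1 requires questioning at each visit. A missing row does not prove that no test would be done.

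What remains is narrower. The backstops capture a bad outcome, not the pregnancy, and they provide no planned follow-up of the newborn. The Step 2 footnote covers gland function only, and no other section names a pregnancy test.

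**Conclusion.** The point holds for female participants. Followed exactly, Sections 8.3 and 7.2.1 require no pregnancy report and no newborn follow-up for a conception in the 8 weeks after the last dose, although the protocol requires contraception throughout them. The trigger spans 5 of 61 days from first dose. This rests on reading study treatment as the five-day everolimus course, which the Glossary and note 5 of Table 7-1 support.

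It also holds, as a separate matter, that the protocol does not show how pregnancy status under exclusion 12 is established before exposure. The only marked eligibility check is about 8 to 11 weeks before dosing, if screening days count from the start of RT and RT ends near RT Day 43.

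The practical size is small. Between 10 and 16 patients are treated. The protocol does not say how many will be women of child-bearing potential; if few are, as seems likely, events would be rare. The reason to act is that a single event could be serious and the wording is cheap to correct.

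**What to change.** 1. In Sections 8.3 and 7.2.1, reconcile the trigger for pregnancy reporting and newborn follow-up with the protocol's own contraception period. For female participants it should run from the first dose to the end of the stated 8 weeks after the last.
2. Leave the collection of partner pregnancy outcomes in Section 8.3 as it is, without a time limit.
3. Reconcile exclusion 12, Table 7-1 with its notes, and the Step 2 eligibility check, so that the protocol shows how pregnancy status is established before exposure. The choice of procedure and timing is for the investigator and sponsor.

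The cost is a written amendment under Section 10, with IRB approval. If item 3 leads to an added safety test, Section 10 lists that among the changes needing approval at each center. The longer trigger itself needs only a little more safety data collection and no new visit, since Visits 6 and 7 already fall either side of the end of the 8 weeks.
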